APPENDIX 4 CRITERIA TO ASSESS SEVERITY OF LIVER-RELATED ADVERSE EVENTS

Parameter	Grade 0	Grade 1	Grade 2	Grade 3	Grade 4
ALT	<1.25	1.25-2.5	>2.5-5.0	>5.0-10	>10
AST	<1.25	1.25-2.5	>2.5-5.0	>5.0-10	>10
Alkaline Phosphatase	<1.25	1.25-2.5	>2.5-5.0	>5.0-10	>10
GGT	<1.25	1.25-2.5	>2.5-5.0	>5.0-10	>10
Bilirubin	Normal	>1.0-1.5	>1.5-2.5	>2.5-5	>5

Abbreviations: ALT = alanine aminotransferase; AST = aspartate aminotransferase; GGT = gamma glutamyl transferase.

NOTE: Values expressed as multiples of the upper limit of the normal range (ULN).

APPENDIX 5 STOPPING RULES FOR LIVER-RELATED BLOOD TESTS

- ALT or AST $>6\times\text{ULN}$ (confirmed with repeat within 24hrs)
- ALT or AST $>5\times\text{ULN}$ for more than 2 weeks
- ALT or AST $>3\times\text{ULN}$ **and** (TBL $>2\times\text{ULN}$ **or** INR >1.5)
- ALT or AST $>3\times\text{ULN}$ with the appearance of fatigue, nausea, vomiting, right upper quadrant pain or tenderness, fever, rash, and/or eosinophilia ($>5\%$)

If ALT or AST elevations do not fall within the above parameters, but are $> 4 \times \text{ULN}$ subject should remain on study drug with close observation which includes:

1. Immediately contacting the CRO medical monitor.
2. Repeating liver enzyme and serum bilirubin tests two or three times weekly.
Frequency of retesting can decrease to once a week or less if abnormalities stabilize or the trial drug has been discontinued and the subject is asymptomatic.
3. Obtaining a more detailed history of symptoms and prior or concurrent diseases.
4. Obtaining a history of concomitant drug use (including nonprescription medications and herbal and dietary supplement preparations), alcohol use, recreational drug use, and special diets.
5. Ruling out acute viral hepatitis types A, B, C, D, and E; autoimmune or alcoholic hepatitis; hypoxic/ischemic hepatopathy; and biliary tract disease., or other disease at the discretion of the investigator
6. Obtaining a history of exposure to environmental chemical agents.
7. Obtaining additional tests to evaluate liver function, as appropriate (eg, INR, direct bilirubin).

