7.2.3.5 Clinical Laboratory Evaluations

All clinical laboratory assays will be performed according to the central laboratory's normal procedures. Reference ranges supplied by the central laboratory will be used to assess the clinical laboratory data for clinical significance and out-of-range pathological changes. The investigator should assess out-of-range clinical laboratory values for clinical significance, indicating if the value(s) is/are not clinically significant or clinically significant. Clinically significant findings should be evaluated for recording as adverse events on the eCRF. Abnormal clinical laboratory values, which are unexpected or not explained by the subject's clinical condition, may, at the discretion of the investigator or sponsor, be repeated as soon as possible until confirmed, explained, or resolved.

The following clinical laboratory assessments will be performed:

Biochemistry

- Albumin (ALB)
- Alkaline phosphatase (ALP)
- Alanine aminotransferase (ALT; SGPT)
- Aspartate aminotransferase (AST; SGOT)
- Blood urea nitrogen (BUN)
- C4
- Calcium (Ca)
- Bicarbonate (CO₂)
- Chloride (Cl)
- Creatinine
- Creatine kinase
- Gamma glutamyl transferase (GGT)
- Glucose
- Lactate dehydrogenase (LDH)
- Magnesium (Mg)
- Phosphate (P)
- Potassium (K)
- Sodium (Na)
- Total and direct bilirubin
- Total cholesterol
- Protein
- Triiodothyronine (T₃)
- Thyroid-stimulating hormone (TSH)
- Triglycerides
- Uric acid

Hematology

- Hemoglobin
- Hematocrit
- Mean corpuscular hemoglobin (MCH)
- Mean corpuscular volume (MCV)
- Platelets
- Red blood cell (RBC)
- White blood cell (WBC) count with differential
- Prothrombin time (PT)
- Activated partial thromboplastin time (aPTT)
- International normalized ratio (INR)

Urinalysis

- Appearance (clarity and color)
- Bilirubin
- Blood
- Glucose
- Ketones
- Leukocyte esterase
- Microscopic examination of sediment
- Nitrite
- pH
- Protein
- Specific gravity
- Urobilinogen
- Oxalate

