9. Current use of any medication (including over-the-counter, herbal, or homeopathic preparations) that could affect the action, absorption, or disposition of the IP, or clinical or laboratory assessment. (Current use is defined as use within 14 days of Screening). Patients currently taking insulin will not be excluded; however, they must be on a stable dose for at least 30 days prior to Screening. Also refer to Section [5.2.2](#), Prohibited Treatment.
10. Use of drugs, herbs or supplements historically associated with causing or worsening NAFLD/NASH for less than 6 months prior to liver biopsy, or initiated any time after liver biopsy performed, including the use of total parenteral nutrition (TPN). Also refer to Section [5.2.2](#), Prohibited Treatment.
11. Serum AST > 5 times upper limit of normal (ULN) at Screening.
12. Serum ALT > 5 times ULN at Screening.
13. Elevated serum creatinine ≥ 2.0 mg/dL.
14. International normalized ratio (INR) > 1.3
15. TB $\geq 2.0 \times$ ULN at Screening (Except for documented Gilbert's syndrome with bilirubin levels 20 μ mol/L to 90 μ mol/L (1.2 to 5.3 mg/dL) and with a ratio of unconjugated/conjugated bilirubin that is commensurately higher).
16. Platelet count $< 130 \times 10^9/L$
17. Medical history of impaired hemostasis or use of anticoagulant medication (low-dose, ie 81 mg, aspirin (ASA) will be allowed).
18. Uncontrolled thyroid disease.
19. Type 1 diabetes mellitus.

20. Known or suspected intolerance or hypersensitivity to the IP, closely-related compounds, or any of the stated ingredients.
21. Known history of alcohol or other substance abuse within the last year or at any time during the study based on investigator's discretion. Refer to Section [7.2.3.8](#), Drug and Alcohol Screening. Weekly alcohol intake greater than 21 grams/day for males and 14 grams/day for females on average or inability to reliably quantify alcohol consumption based on investigator's judgment.
22. Within 6 months of MRI and liver biopsy:
 - Have used any IP
 - Have been enrolled in a clinical study (including vaccine studies) that, in the investigator's opinion, may impact this Shire-sponsored study
23. Inability to safely obtain a liver biopsy.
24. The anticipated need for a surgical procedure during the study that could interfere with the treatment.
25. Known positivity for human immunodeficiency virus (HIV) infection.

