APPENDIX 5 STOPPING RULES FOR LIVER-RELATED BLOOD TESTS

- ALT or AST $>6\times$ ULN (confirmed with repeat within 24hrs)
- ALT or AST $>5\times$ ULN for more than 2 weeks
- ALT or AST $>3\times$ ULN **and** (TBL $>2\times$ ULN **or** INR >1.5)
- ALT or AST $>3\times$ ULN with the appearance of fatigue, nausea, vomiting, right upper quadrant pain or tenderness, fever, rash, and/or eosinophilia ($>5\%$)

If ALT or AST elevations do not fall within the above parameters, but are $> 4 \times$ ULN subject should remain on study drug with close observation which includes:

1. Immediately contacting the CRO medical monitor.
2. Repeating liver enzyme and serum bilirubin tests two or three times weekly.
Frequency of retesting can decrease to once a week or less if abnormalities stabilize or the trial drug has been discontinued and the subject is asymptomatic.
3. Obtaining a more detailed history of symptoms and prior or concurrent diseases.
4. Obtaining a history of concomitant drug use (including nonprescription medications and herbal and dietary supplement preparations), alcohol use, recreational drug use, and special diets.
5. Ruling out acute viral hepatitis types A, B, C, D, and E; autoimmune or alcoholic hepatitis; hypoxic/ischemic hepatopathy; and biliary tract disease., or other disease at the discretion of the investigator
6. Obtaining a history of exposure to environmental chemical agents.
7. Obtaining additional tests to evaluate liver function, as appropriate (eg, INR, direct bilirubin).

APPENDIX 6 **GENERAL PRINCIPLES AND SPECIFIC RULES FOR DOSE DISCONTINUATION AT 24 WEEK INTERIM ANALYSIS – GUIDANCE FOR DATA MONITORING COMMITTEE ONLY**

General Principles

A net positive benefit risk assessment on HFF takes precedence over effectiveness on ALT. Covers the situations when 2 doses show net positive benefit risk on HFF and 1 dose shows positive or net positive benefit risk on ALT.

Choose the dose(s) that have the largest difference in dose from amongst those exhibiting a net positive benefit risk.

As a minimally absorbed drug, volixibat at higher doses is less likely than absorbed drugs to exhibit additional TEAEs in large longer duration trials that were not seen in smaller shorter trials.

Specific Rules

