9. Current use of any medication (including over-the-counter, herbal, or homeopathic preparations) that could affect the action, absorption, or disposition of the IP, or clinical or laboratory assessment. (Current use is defined as use within 14 days of Screening). Patients currently taking insulin will not be excluded; however, they must be on a stable dose for at least 30 days prior to Screening.
10. Use of drugs, herbs or supplements historically associated with causing or worsening NAFLD/NASH for less than 6 months prior to liver biopsy, or initiated any time after liver biopsy performed, including the use of total parenteral nutrition (TPN).
11. Serum AST > 5 times upper limit of normal (ULN) at Screening.
12. Serum ALT > 5 times ULN at Screening.
13. Elevated serum creatinine ≥ 2.0 mg/dL.
14. International normalized ratio (INR) > 1.3
15. TB $\geq 2.0 \times$ ULN at Screening (Except for documented Gilbert's syndrome with bilirubin levels 20 μ mol/L to 90 μ mol/L (1.2 to 5.3 mg/dL) and with a ratio of unconjugated/conjugated bilirubin that is commensurately higher).
16. Platelet count $< 130 \times 10^9/L$
17. Medical history of impaired hemostasis or use of anticoagulant medication (baby aspirin (ASA) will be allowed).
18. Uncontrolled thyroid disease.

19. Type 1 diabetes mellitus.
20. Known or suspected intolerance or hypersensitivity to the IP, closely-related compounds, or any of the stated ingredients.
21. Known history of alcohol or other substance abuse within the last year. Weekly alcohol intake greater than 21 units for males and 14 units for females on average or inability to reliably quantify alcohol consumption based on investigator's judgment.
22. Within 6 months of MRI and liver biopsy:
 - Have used any IP
 - Have been enrolled in a clinical study (including vaccine studies) that, in the investigator's opinion, may impact this Shire-sponsored study
23. Inability to safely obtain a liver biopsy.
24. The anticipated need for a surgical procedure during the study that could interfere with the treatment.
25. Known positivity for human immunodeficiency virus (HIV) infection.
26. Cancer within 5 years of Screening, except for basal or squamous cell carcinoma of the skin or in situ cervical carcinoma that has been treated with no evidence of recurrence.

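### Appendix 5's third stopping rule makes no provision for Gilbert's syndrome, so in Amendment 1 and the original protocol some eligible subjects meet it with unchanged entry values

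*Protocol*

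**What the plan says.** The document contains part of Amendment 2, then Amendment 1 and the original protocol. The four bullets of Appendix 5 are called rules 1 to 4 here, in the order printed.

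**Stopping rule.** Rule 3 in Amendment 2 and in the original is "ALT or AST $>3\times\text{ULN}$ and (TBL $>2\times\text{ULN}$ or INR >1.5". Amendment 1 has the same rule: "ALT or AST $>3\times$ ULN and (TBL $>2\times$ ULN or INR >1.5". Section 4.5.4 (Amendment 1) refers to Appendix 5 as stopping rules. Section 8.1.6 refers to it as guidelines.

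**Entry limits (Section 4.2, Amendment 1 and original).**
- Exclusion 11: "Serum AST > 5 times upper limit of normal (ULN) at Screening".
- Exclusion 12: "Serum ALT > 5 times ULN at Screening".
- Exclusion 14: INR above 1.3.
- Exclusion 15: total bilirubin of 2.0×ULN or more at Screening, with the carve-out "Except for documented Gilbert's syndrome with bilirubin levels" of 20 to 90 µmol/L (1.2 to 5.3 mg/dL). The carve-out also requires a ratio of "unconjugated/conjugated bilirubin that is commensurately higher".

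**Direct bilirubin.** Section 7.2.3.5 lists "Total and direct bilirubin" in the biochemistry panel, which Section 7.1.3 schedules at every treatment visit. Within Appendix 5, direct bilirubin appears only under close observation, for subjects who met no stopping rule: "Obtaining additional tests to evaluate liver function, as appropriate (eg, INR, direct bilirubin".

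**The concern.** Exclusion 15 deliberately admits people whose raised bilirubin is explained by Gilbert's syndrome. Rule 3 then treats that same raised total bilirubin as one half of a liver-injury signal. The other half, ALT or AST above 3×ULN, is also allowed at entry, up to 5×ULN. Such a subject can therefore meet a stopping rule at the first on-treatment blood test, at Week 2, although nothing has changed.

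Two things are at stake. The subject may lose treatment for a finding that the protocol accepted at enrolment. The trial may also lose a primary-endpoint observation: Sections 4.5 and 7.1.3 do not require the end-of-study biopsy after discontinuation before Week 44, and Section 4.5 (Amendment 1) says that discontinued subjects are not replaced. Because Appendix 5 is called rules in one section and guidelines in another, sites may also handle the same subject differently.

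**Working it through.** **1. The plan's own figure.** Using 17.1 µmol/L per mg/dL, 20/17.1 = 1.17 and 90/17.1 = 5.26. The stated window of 1.2 to 5.3 mg/dL is reproduced.

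**2. Does the window reach above rule 3's bilirubin limit?** The bilirubin ULN is not stated. The top of the window exceeds 2×ULN whenever ULN < 5.3/2 = 2.65 mg/dL. For a range of assumed ULNs:

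| Assumed ULN (mg/dL) | 2×ULN (mg/dL) | 5.3 mg/dL as a multiple of ULN |
|---|---|---|
| 1.0 | 2.0 | 5.3 |
| 1.2 | 2.4 | 4.4 |
| 1.3 | 2.6 | 4.1 |
| 1.5 | 3.0 | 3.5 |

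The exemption has an effect only at 2×ULN or more. Anyone who needs it therefore already meets the bilirubin condition of rule 3, except at exactly 2.0×ULN.

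**3. Entry limits against the stopping rules (Amendment 1; the original pairs the same limits).**

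| Stopping condition | Entry limit | Met with entry values? |
|---|---|---|
| Rule 1: ALT or AST >6×ULN | ≤5×ULN | No |
| Rule 2: ALT or AST >5×ULN for more than 2 weeks | ≤5×ULN | No |
| Rule 3, INR: ALT or AST >3×ULN and INR >1.5 | INR ≤1.3 | No |
| Rule 3, bilirubin, without Gilbert's: ALT or AST >3×ULN and total bilirubin >2×ULN | bilirubin <2×ULN | No |
| Rule 3, bilirubin, documented Gilbert's | ALT and AST ≤5×ULN; bilirubin up to 5.3 mg/dL | Yes, if ALT or AST >3×ULN and bilirubin >2×ULN |
| Rule 4: ALT or AST >3×ULN plus newly appearing symptoms, rash or eosinophilia | – | Needs a new finding |

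A grid check in steps of 0.1 (assumed ULN 1.2 mg/dL, INR held at 1.3) agrees. It finds no overlap without Gilbert's syndrome. With it, the overlap covers ALT or AST of 3.1 to 5.0×ULN with bilirubin of 2.5 to 5.3 mg/dL.

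**4. Does anything in Appendix 5 rescue these subjects?** No. Close observation on drug, for ALT or AST above 4×ULN, opens only if no stopping rule is met. Take two subjects with a stable ALT of 4.5×ULN: the one without Gilbert's syndrome stays on drug under observation, while the one with it and bilirubin above 2×ULN meets rule 3. Unlike rule 1, rule 3 asks for no confirmatory repeat.

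**5. Would direct bilirubin above 2×ULN alone solve it?** The direct-bilirubin ULN is not stated. Assuming 0.2 to 0.4 mg/dL, the trigger is 2 × 0.2 = 0.4 to 2 × 0.4 = 0.8 mg/dL. At a total of 5.3 mg/dL that is a direct share of 0.4/5.3 = 8% to 0.8/5.3 = 15%. A subject could already exceed this at entry, so the substitute needs a baseline condition as well.

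**The case against.** The strongest objection concerns the version. Amendment 2 is the latest listed in Appendix 1, and its Section 4.2 is not among the pages available. A reader might infer that the current protocol contradicts itself. The documents do not support that: both complete pairs of entry limits and rule 3 are in superseded versions. Amendment 2 did rewrite other sections, such as the analysis-set definitions, so carry-over cannot be presumed. This objection stands, and for Amendment 2 the point is a question to the sponsor.

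Second, an absolute stop may be deliberate caution. Section 1.3 (Amendment 1) reports a Phase 1 serious event of raised ALT judged related to volixibat, and an entry exemption promises no continued dosing. That is a fair reading of intent, but the layout argues against it. Every other stopping condition is kept clear of the entry limits, and only the Gilbert's exemption breaks the pattern.

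Third, a reader might infer an automatic stop at Week 2. The text leaves more room. Section 8.1.6 speaks of guidelines, exclusion 28 lets an investigator decline a subject on safety grounds, and Section 4.5 encourages discussing withdrawal with the medical monitor. These provisions make an unnoticed stop less likely, but they do not change rule 3.

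Fourth, a reader might infer a material loss of primary-endpoint data. Nothing shows this. The number of such subjects is not given and may be zero, and a biopsy after early discontinuation is not required but also not forbidden.

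**Conclusion.** The point holds for Amendment 1 and the original protocol. An eligible subject with documented Gilbert's syndrome, total bilirubin above 2×ULN and ALT or AST above 3 and up to 5×ULN meets rule 3 with no change from entry. For Amendment 2 it is a query, because rule 3 is unchanged but the entry limits cannot be seen.

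Severity is minor. The group is narrow, its size is unknown, and no effect on the primary analysis can be estimated. Gilbert's subjects with bilirubin at or below 2×ULN, or with both ALT and AST at or below 3×ULN, do not meet the rule at entry values. The conclusion assumes a bilirubin ULN below 2.65 mg/dL. A stop at Week 2 further assumes that Screening values, taken up to 56 days before baseline, persist.

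**What to change.** First confirm that Section 4.2 of Amendment 2 still carries exclusions 11, 12 and 15 as in Amendment 1. If so, add one note to rule 3, for documented Gilbert's syndrome only:

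- Read the bilirubin condition as direct bilirubin above 2×ULN **and** above the subject's own baseline direct bilirubin, by a margin set by the sponsor's safety physician.
- Require prompt medical-monitor review whenever ALT or AST is above 3×ULN and total bilirubin is above 2×ULN.

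Leave the INR condition and rules 1, 2 and 4 unchanged. The use of direct bilirubin follows the exemption's own condition, which already relies on the unconjugated/conjugated ratio.

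The cost is one note and some medical-monitor time. No new test is needed, since direct bilirubin is in the panel drawn at baseline and at every treatment visit. The downside is that a true liver signal in a Gilbert's subject might lead to a slightly later stop. The medical-monitor review, the INR condition and the other three rules limit that risk.

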I understand that the information in this protocol is confidential and should not be disclosed, other than to those directly involved in the execution or the scientific/ethical review of the study, without written authorization from the sponsor. It is, however, permissible to provide the information contained herein to a subject in order to obtain their consent to participate.

I agree to conduct this study according to this protocol and to comply with its requirements, subject to ethical and safety considerations and guidelines, and to conduct the study in accordance with International Conference on Harmonisation guidelines on Good Clinical Practice and with the applicable regulatory requirements.

I understand that failure to comply with the requirements of the protocol may lead to the termination of my participation as an investigator for this study.

I understand that the sponsor may decide to suspend or prematurely terminate the study at any time for whatever reason; such a decision will be communicated to me in writing. Conversely, should I decide to withdraw from execution of the study I will communicate my intention immediately in writing to the sponsor.

Investigator Name and Address:

(please hand print or type)

Investigator Name and Address:
(please hand print or type)

Signature:

Date:

SUMMARY OF CHANGES FROM PREVIOUS VERSION

Protocol Amendments		
Summary of Change(s) Since Last Version of Approved Protocol		
Amendment Number	Amendment Date	Global/Country/Site Specific
1	8 April 2016	Global
Description of Change		Section(s) Affected by Change
Emergency Contact Information updated		Emergency Contact Information
Abbreviations list updated		Abbreviations
Requirement for meal fat content of 10-20 grams before daily dose of investigational product added		Synopsis Table 1 Schedule of Assessments Sections 6.2.3, 7.1.3
Inclusion Criterion #6 clarified fibrosis stage F1-F3		Synopsis Section 4.1
Exclusion Criterion #6 shortened sentence for clarity		Synopsis Section 4.2
Exclusion Criterion #7 cross referenced to Section 5.2.1 Permitted Treatment		Synopsis Section 4.2
Exclusion Criterion #9 referred to Section 5.2.2 Prohibited Treatment		Synopsis Section 4.2
Exclusion Criterion #17 dose for current use of low-dose aspirin (81 mg) allowed		Synopsis Section 4.2
Exclusion Criterion #21 clarified weekly alcohol intake measurement from units to grams/day; added statement that subjects could be excluded at any time during the study based on investigator discretion due to alcohol or substance abuse		Synopsis Section 4.2
Planned duration of screening period increased from 42 to 56 days		Synopsis Table 1 Schedule of Assessments Sections 7.1, 7.1.1, 7.1.2
Secondary endpoint of MRI-HFF clarified for subjects included in the IA		Synopsis
Primary hypothesis was clarified to Null and Alternative hypotheses		Synopsis Section 9.6
Clarified that NAS \geq 6 is 6, 7, 8		Synopsis Sections 6.2.2
Screening period changed from -6 to -8 weeks		Table 1 Schedule of Assessments Section 3.1 Figure 1 Sections 7.1, 7.1.1
Footnote deleted for ECG; all subsequent footnotes revised		Table 1 Schedule of Assessments
Footnote 1 revised serum pregnancy test from reflex to serum β -HCG		Table 1 Schedule of Assessments
Reference to Karpen oral presentation at AASLD added		Sections 1.2, 1.3

Inclusion Criterion #4 added cross reference to Section 4.4 Reproductive Potential	Section 4.1
Exclusion Criteria #9 and #10 added cross reference to Section 5.2.2 Prohibited Treatment	Section 4.2
Exclusion Criterion #21 added cross reference to Section 7.2.3.8 Drug and Alcohol Screening	Section 4.2
Acceptable methods of contraception were modified to delete the use of double-barrier methods and clarify barrier methods, add male sterilization, add and define abstinence	Section 4.4.1 Section 4.4.2
Deleted statement regarding withdrawal of subjects for missing >3 consecutive days of dosing	Section 4.5
Redefined PVRM physician as PVRM Medical Lead	Section 4.5.4
Additional permitted medications and supplements were further defined and sponsor medical monitor was redefined as Shire GCDL	Section 5.2.1
Additional prohibited over-the-counter and herbal therapies were specified and a note was added that the list is not comprehensive	Section 5.2.2
Dosing statement deleted from Section 6.2 and moved to Section 6.2.3	Sections 6.2, 6.2.3
Clarified that NAS \geq 6 is 6, 7, 8; text modified to specify randomization after the Week 24 IA would be equally allocated to all remaining doses.	Section 6.2.2
Text deleted “For blinded studies, there will be a provision for unblinding to ensure adequate treatment of the subject in the case of an emergency.”	Section 6.2.4
Process for drug return or destruction was further clarified	Section 6.4
